6.7.1. Toxicity Rules for Adverse Events Deemed Related to Study Drug

These rules apply to AEs that are assessed as related to study drug by the Investigator. Dose continuation or escalation will proceed as scheduled (Table 7) and the study will continue as planned provided no prespecified toxicity events occur.

- The entire study will be suspended if any life-threatening (Common Terminology Criteria for Adverse Events [CTCAE] v4.03; published 14 Jun 2010, Grade 4) or fatal (CTCAE Grade 5) SAEs occur. If any of the following occur, dosing within the affected cohort will be suspended and dose escalation cannot commence. Interim lower doses may be subsequently administered at the discretion of the SRC.
 - A treatment-related SAE, irrespective of the CTCAE grade, in 1 subject. This includes any subject potentially meeting the criteria for Hy's Law $(ALT \ge 3 \times ULN)$ and bilirubin $\ge 2 \times ULN$ (ie, > 35% direct bilirubin) or $ALT \ge 3 \times ULN$ and international normalized ratio (INR) > 1.5, if INR was measured, which may indicate severe liver injury (possibly Hy's Law).
 - Severe (CTCAE Grade 3) nonserious treatment-related AEs in 2 subjects in the same cohort, independent of whether the AEs are within the same System Organ Class (SOC).

For Cohorts 2 through 4 (ravulizumab SC/rHuPH20):

- Any number of Grade 1 ISRs are permitted to allow continuation of dosing within a cohort and escalation to the next highest dose level.
- Any number of Grade 2 ISRs that have resolved or reduced to Grade 1 by the time of the minimum data review period (168 hours post-dose) are permitted to allow continuation of dosing within a cohort and escalation to the next highest dose level.
- If, at the end of the minimum data review period (168 hours post-dose) there are more than 2 subjects with ISRs that are still Grade 2, dose escalation cannot occur and the period of observation should be extended by a further 168 hours (or shorter, if all subjects recover to at least Grade 1 before that time point). If all affected subjects show sign of recovery (at least to Grade 1), dose escalation can then proceed. If all affected subjects remain at Grade 2 after the additional 168-hour observation period, the SRC will make the decision to either prolong further the observation period or progress to subsequent combination cohorts at a lower dose/smaller volume of study drug.

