6.1. Study Drug Administered

The study drug composition and doses to be administered in this study are presented in Table 6.

Ravulizumab IV Ravulizumab SC rHuPH20 Ravulizumab Study Drug Name: SC/rHuPH20 Dosage Ravulizumab IV is Ravulizumab SC rHuPH20 is Ravulizumab Formulation: formulated at pH 7.0 is formulated at supplied as SC/rHuPH20 is and each vial pH 7.4 and each ENHANZE® drug formulated per the contains 300 mg of vial contains product (EDP) is individual ravulizumab in 1100 mg of supplied in vials as components of the ravulizumab in 10 mM sodium a sterile, singledrug product. phosphate, 150 mM 50 mM sodium dose, injectable liquid at sodium chloride, phosphate, 25 0.02% polysorbate mM arginine, 5% approximately sucrose, and 110 kU/mL. The 80. 0.05% solution has a pH of 6.5 and contains Each vial contains polysorbate 80. 10 mg/mL. 130 mM sodium chloride, 10 mM Each vial contains 100 mg/mL. L-Histidine/ hydrochloride as a buffer. 10 mM L-Methionine. and 0.2% w/w polysorbate 80. The solution is filled to 0.5 mL in a 2-mL glass vial. ravulizumab SC Unit Dose 400 mg 400 mg NA 500 mg/rHuPH20 Strength(s)/ Dosage Level(s): 10,000 units ravulizumab SC 1000 mg/rHuPH20 20,000 units ravulizumab SC 2000 mg/rHuPH20 40,000 units SC SC IV Route of SC Administration

 Table 6:
 Dose Reference Chart for Study ALXN1210-HV-105

Study Drug Name:	Ravulizumab IV	Ravulizumab SC	rHuPH20	Ravulizumab SC/rHuPH20
Dosing Instructions:	A single dose of ravulizumab IV will be administered via IV infusion and 80 mL of ravulizumab IV will be administered at a maximum infusion rate of 333mL/hr, for a minimum infusion duration of approximately 15 minutes. Use of an in-line filter for infusion is required.	A single dose of ravulizumab SC will be administered via SC infusion administered by a syringe pump. The total volume to be administered will be 4 mL at an infusion rate of 0.5 mL/min.	NA	Ravulizumab will be co-mixed with EDP in empty, sterile 20-mL glass vials. A single dose of ravulizumab SC/rHuPH20 will be administered via SC infusion, administered via an infusion pump. The total volume to be administered for the combination cohorts will be 5.23 mL in Cohort 2, 10.46 mL in Cohort 3, and 20.91 mL in Cohort 4 at an infusion rate of 2 mL/min

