6.7. Dose Modification

Decisions to continue, modify (explore the dose cohort further), or escalate dosing will be made by the Investigator and/or SRC as described in Table 7. The SRC may also make recommendations regarding safety issues, study conduct, or study suspension. The SRC is composed of the Sponsor's medical monitor, biostatistician, pharmacovigilance representative, clinical pharmacologist, and the Investigator. The membership roster, schedule of meetings, data required for each safety review, and requirements for documenting meeting discussions and outcome will be outlined in the SRC charter.

The SRC will review all available safety and tolerability data from a given cohort for at least the first 168 hours after study drug administration in order to determine whether to escalate the ravulizumab SC/rHuPH20 dose and initiate the next cohort. Data through 168 hours must be available for at least 11 of the 12 subjects. Dose escalation or modification will occur based on the recommendation of the SRC to dose escalate and only applies to Cohort 3 and Cohort 4.

Dosing Decision	Responsib le Party	Data to be Reviewed	Documentation/Communication Methods
Continuation from the sentinel subject to the remaining subjects in Cohort 1	Investigato r	A minimum of 24 hours post- dose safety and tolerability data from the sentinel subject.	The Investigator will document the decision in an email to the Sponsor. The email does not require the Sponsor's response, unless there is disagreement with the Investigator's decision.
Continuation from the sentinel subjects to the remaining subjects in Cohort 2	Investigato r	A minimum of 24 hours post- dose safety and tolerability data from the sentinel subjects.	The Investigator will document the decision in an email to the Sponsor. The email does not require the Sponsor's response, unless there is disagreement with the Investigator's decision.
Escalation to Cohort 3	SRC	A minimum of 168 hours post- dose safety and tolerability data from at least 11 subjects (all of whom have received treatment) from the previous cohort that was on the next lowest dose level (and hence, next lowest exposure) of ravulizumab SC/rHuPH20.	The SRC will document the decision on the escalation/progression approval form.

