8.3.6. Management of Potential Adverse Events During Study Drug Administration

Infusion of other monoclonal antibodies has been associated with infusion reactions, with onset typically during or shortly after completion of the infusion. For this reason, subjects will be carefully observed during each infusion.

Subjects will be closely monitored during and after study drug administration for any symptoms of anaphylaxis and other hypersensitivity reactions, including circulatory and/or respiratory changes or arrest, or urticaria, arthralgias, myalgias, or other signs of related reactions. Adequate treatment will be immediately available. Infusion-associated AEs may occur, and depending on their type and severity, discontinuation of infusion may be required. Subjects will be informed of early symptoms and signs of hypersensitivity reactions including hives, swollen face, eyelids, lips, or tongue, or trouble with breathing. An acute infusion reaction algorithm will be used to manage infusion-related reactions (Section 10.7 [Appendix 6: Acute Infusion Reactions Algorithm]). In this study, regular assessments to monitor infusion reactions and infusion-site reactions will be done. To ensure that reactions can be dealt with promptly, there will be at least 15 minutes between the end of IV/SC infusion in 1 subject and the start of IV/SC infusion in the next subject. No more than 6 subjects assigned to receive ravulizumab IV will be dosed per day. Any reactions will be treated and taken into account in the dose continuation/escalation and toxicity rules (Table 7). If anaphylactic reactions occur, the current "UK Treatment Guideline for Anaphylactic Reactions" of the UK Resuscitation Council will be followed (Section 10.7 [Appendix 7: United Kingdom Resuscitation Council Anaphylaxis Algorithm]).

Subjects who experience a severe reaction during administration of study drug that results in discontinuation of study drug should undergo all scheduled safety, immunogenicity, PK, and PD evaluations required by the protocol. Subjects will therefore be instructed to attend all scheduled visits and undergo all procedures per protocol.

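### At the sentinel step, the two-subject trigger for nonserious related Grade 3 AEs cannot be met in Cohort 1 and needs both sentinels in Cohorts 2-4, so no prespecified rule requires a hold after one such event

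*Protocol*

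**What the plan says.** Section 6.7.1 of the protocol sets the toxicity rules for AEs that the Investigator judges related to study drug. They govern both continuation within a cohort and escalation: "Dose continuation or escalation will proceed as scheduled (Table 7) and the study will continue as planned provided no prespecified toxicity events occur". Two events suspend dosing in the affected cohort: "A treatment-related SAE, irrespective of the CTCAE grade, in 1 subject", which includes potential Hy's Law cases, and "Severe (CTCAE Grade 3) nonserious treatment-related AEs in 2 subjects in the same cohort". A related Grade 4 or 5 SAE suspends the whole study. For Cohorts 2-4, further bullets on injection site reactions (ISRs) set terms for Grades 1 and 2 only.

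Section 6.3 places one sentinel in a cohort of 6 and two in a cohort of 12, for Cohorts 1-4. The rest of the cohort follows at least 24 hours later.

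Table 7 (Section 6.7) makes the Investigator responsible for moving from sentinels to the rest of the cohort. In Cohort 1 the data required are "A minimum of 24 hours post- dose safety and tolerability data from the sentinel subject"; Cohorts 2-4 have the same minimum for both sentinels. The Investigator emails the decision to the Sponsor, and "The email does not require the Sponsor's response, unless there is disagreement with the Investigator's decision". The SRC is the named decision-maker only for escalation to Cohorts 3 and 4, but Section 6.7 also lets it make recommendations on safety issues and suspension.

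Section 8.3.6 directs that reactions be weighed when the continuation, escalation and toxicity rules are applied. On spacing it requires "at least 15 minutes between the end of IV/SC infusion in 1 subject and the start of IV/SC infusion in the next subject", and "No more than 6 subjects assigned to receive ravulizumab IV will be dosed per day".

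**The concern.** The two-subject rule is sized for a full cohort of 6 or 12, yet Section 6.7.1 also applies it where only one or two subjects have been exposed. At that step it does almost no work. A single related, nonserious Grade 3 AE in a sentinel is not a prespecified toxicity event, so the text leans towards continuing unless the Investigator decides otherwise. Under Section 6.7.1 the Investigator also judges whether the event is related.

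Appendix 3 describes a Grade 3 event as one that incapacitates and prevents normal activity. The subjects are healthy volunteers with no direct benefit. Section 4.2 justifies sentinel dosing because this is the first use of the combination, and the first time 400 mg SC is given as one infusion. The dose cannot be withdrawn, and the expected half-life at the highest SC dose is about 42 days.

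Once the sentinel step is passed, the two-subject rule protects the remaining subjects only if a second event appears while some are still undosed. The written SC spacing is short, and the daily cap applies only to IV dosing.

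**Working it through.** The plan states no operating characteristic for this rule, so there is no figure to reproduce. The main result is a count and needs no event rate.

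**1. Can the trigger be met at the sentinel step?** It needs 2 affected subjects in the cohort.

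- Cohort 1: 1 sentinel dosed, so 2 affected is impossible.
- Cohorts 2, 3 and 4: 2 sentinels dosed, so both must be affected.

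**2. Does another rule cover one event?**

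- The one-subject trigger in 6.7.1 covers related SAEs, including potential Hy's Law cases.
- The study-wide stop covers related Grade 4 or 5 SAEs.
- The ISR bullets permit Grade 1 and resolving Grade 2 reactions. A Grade 3 ISR in Cohorts 2-4 is arguably not permitted, but no bullet says so.
- Section 8.3.6 directs attention to reactions without a threshold.
- Section 6.7 allows SRC recommendations but does not require SRC review at this step. It describes the SRC charter, which is not among the documents, as covering membership, meetings, data required and documentation.

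None sets a one-subject threshold for a nonserious related Grade 3 AE.

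**3. Size.** Let p be the probability that a sentinel has a related, nonserious Grade 3 AE by the time of the decision. The documents give no value, so 1%, 5% and 10% are assumed, the same in every cohort, with subjects independent.

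| p | Trigger met, 2 sentinels: p² | Exactly one affected: 2p(1-p) | Trigger met, Cohort 1 |
|---|---|---|---|
| 0.01 | 0.0001 | 0.0198 | 0 |
| 0.05 | 0.0025 | 0.095 | 0 |
| 0.10 | 0.01 | 0.18 | 0 |

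Over a full cohort the same rule does have power to fire. The probability of at least 2 affected is 0.033 (n = 6) and 0.118 (n = 12) at p = 0.05, and 0.114 and 0.341 at p = 0.10.

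**4. Holds added by a one-event rule.** If all four sentinel cohorts enroll, the expected number is p + 3 × 2p(1-p):

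- p = 0.01: 0.01 + 3 × 0.0198 = 0.069
- p = 0.05: 0.05 + 3 × 0.095 = 0.335
- p = 0.10: 0.10 + 3 × 0.18 = 0.640

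The chance of at least one is 1 - (1-p)(1-2p(1-p))³ = 0.068, 0.296 and 0.504. All of these are upper bounds, because they count a hold as added even where the Investigator would have paused anyway.

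**5. Shortest time to dose the rest of a cohort.** Table 6 gives 4 mL at 0.5 mL/min for Cohort 1 and "5.23 mL in Cohort 2, 10.46 mL in Cohort 3, and 20.91 mL in Cohort 4 at an infusion rate of 2 mL/min" for the others. With n subjects remaining, the minimum is n × volume/rate + (n-1) × 15 min:

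- Cohort 1: 5 × 8.0 + 4 × 15 = 100 min (1.7 h)
- Cohort 2: 10 × 2.615 + 9 × 15 = 161 min (2.7 h)
- Cohort 3: 10 × 5.23 + 9 × 15 = 187 min (3.1 h)
- Cohort 4: 10 × 10.455 + 9 × 15 = 240 min (4.0 h)

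These are the shortest times the written spacing allows for one cohort alone. If the 15 non-sentinels of Cohorts 1 and 2 shared one queue, the minimum would be 5 × 8.0 + 10 × 2.615 + 14 × 15 = 276 min (4.6 h).

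**The case against.** The strongest reply is that the sentinel step has its own control. Table 7 requires an affirmative, documented Investigator decision, Section 8.3.6 requires reactions to be weighed, the Sponsor can object and the SRC can recommend suspension. On this view the two-subject rule was meant for the cohort, and medical judgement suits a step with one or two subjects. This stands as a description of the safeguards. It does not explain why 6.7.1 fixes hard stops for continuation and then leaves this class of event without one where information is thinnest.

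The residual class is also narrow. Subjects are inpatients through Day 5. Under Appendix 3, prolonged hospitalization is serious, doubt about hospitalization resolves to serious, and important medical events are usually serious. Some incapacitating related events would therefore be SAEs and stop the cohort after one subject. This lowers the plausible p but does not close the gap.

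Prior exposure is reassuring. Table 5 puts the margins against 800 mg IV every 4 weeks at 2.1 to 8.2 for Cmax and 3.4 to 13.4 for AUC. Section 2.1 reports single rHuPH20 doses up to 96,000 units, against 40,000 at most here. The 400 mg SC dose of Cohort 1 has been given before, as four injections. This too favors the low end of the assumed rates.

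Finally, the protocol says dosing will be staggered within and between cohorts and gives no schedule, so actual dosing may be much slower than the minimum times. That is correct, and those times show only what the text permits.

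**Conclusion.** The point holds as a gap in the prespecified rules. For nonserious related Grade 3 AEs, the written trigger cannot be met at the Cohort 1 sentinel step and needs two of two in Cohorts 2-4. After one such event, a hold depends on judgement. This follows from the counts and does not rest on any assumed rate.

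A reader might infer more than the documents support:

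- *That dosing continues regardless.* It does not, because Table 7 needs a positive Investigator decision.
- *That the sentinel event is lost.* It stays in the cohort count, so a second related Grade 3 AE would suspend dosing.
- *That any severe sentinel event escapes the rules.* Related SAEs, potential Hy's Law cases and arguably Grade 3 ISRs in Cohorts 2-4 do not.
- *That the probabilities measure harm, or that all subjects will be dosed within hours.* The probabilities describe the written trigger under assumed rates, and the times are permitted minimums.

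With other safeguards in place and low rates more plausible, this is a cheap improvement to subject safety and not a fault that invalidates the design.

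**What to change.** Add to Section 6.7.1, and as a matching phrase in the four sentinel rows of Table 7: any related Grade 3 AE in a sentinel subject before the remaining subjects are dosed holds dosing in that cohort until the SRC has reviewed the event and recorded its decision. Keep the two-subject rule unchanged for the full cohort.

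The text cost is one sentence and four short phrases. No new committee is needed: the existing SRC already includes the Investigator, and it adds the Sponsor's medical monitor, pharmacovigilance representative, clinical pharmacologist and biostatistician to the decision.

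The operating cost is an occasional pause. Remaining subjects may by then be admitted, on antibiotics from the evening of Day -1 and inside the 7-day randomization window, so a pause could mean re-admission and repeated Day -1 checks. A prompt ad hoc SRC review would limit this.

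### The injection-site-reaction stop lapses when a reaction is worse: three subjects at Grade 2 block escalation, but two at Grade 2 plus one at nonserious Grade 3 trip no rule

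*Protocol*

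**What the plan says.** Protocol Section 6.7.1 sets the toxicity rules for adverse events judged related to study drug. It opens with a default: "Dose continuation or escalation will proceed as scheduled (Table 7"), provided no prespecified toxicity event has occurred. The rules that can stop escalation are these:

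- **Grade 4 or 5 serious events:** "The entire study will be suspended if any life-threatening" or fatal serious adverse event (SAE) occurs.
- **Any related SAE:** "A treatment-related SAE, irrespective of the CTCAE grade, in 1 subject" suspends the affected cohort and bars escalation.
- **Nonserious Grade 3:** "Severe (CTCAE Grade 3) nonserious treatment-related AEs in 2 subjects in the same cohort" does the same.
- **ISRs, Cohorts 2 to 4:** Grade 1 reactions are permitted in any number, as are Grade 2 reactions that have fallen to Grade 1 or resolved by 168 hours. If at that point "there are more than 2 subjects with ISRs that are still Grade 2, dose escalation cannot occur", and observation is extended by up to another 168 hours.

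After the extension two outcomes are described. One is full recovery: "If all affected subjects show sign of recovery (at least to Grade 1), dose escalation can then proceed". The other is that nobody has improved: "If all affected subjects remain at Grade 2 after the additional 168-hour observation period", in which case the SRC either prolongs observation or moves on at a lower dose or smaller volume. No ISR bullet mentions Grade 3.

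Section 6.7 adds the backstop: "Dose escalation or modification will occur based on the recommendation of the SRC to dose escalate". Table 7 assigns both escalation decisions, to Cohort 3 and to Cohort 4, to the SRC.

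**The concern.** A stopping rule should be monotone in severity: if a cohort is held in one state, it should also be held in any state that is at least as bad. This rule is not. A subject whose reaction is at Grade 3 drops out of the Grade 2 count, and one subject is too few for the Grade 3 rule. Worsening can therefore lift a hold.

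The ISR rule is the local-tolerability stop written specifically for the combination cohorts. It stands before each doubling of dose (500 to 1000 to 2000 mg) and of infused volume (5.23 to 10.46 to 20.91 mL, Table 6). The combination has not been given to humans before (Sections 2.3.4 and 4.3), and the healthy volunteers receive no direct benefit (Section 2.3).

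There is a smaller gap after the extended observation. The text covers all affected subjects recovered and all still at Grade 2, but not a mixture.

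**Working it through.** The plan gives no operating characteristics for these rules, so there is no figure to reproduce. The check is of the logic.

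**Inputs.** All are from Protocol Sections 6.7 and 6.7.1. Let *a* be the number of subjects with a related ISR at Grade 2 at 168 hours, *b* the number at nonserious Grade 3, and *n* the subjects reviewed (12 per combination cohort, with a minimum of 11). No other related Grade 3 event, SAE or Grade 4/5 event is assumed.

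- Written rule: blocked if *a* > 2 or *b* ≥ 2.
- Rule counting Grade 2 or higher: blocked if *a* + *b* > 2 or *b* ≥ 2.

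**Key states.**

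| Grade 2, Grade 3 | Written rule | Grade 2-or-higher count |
|---|---|---|
| (3, 0) | blocked: 3 > 2 | blocked |
| (2, 1) | **not blocked**: 2 is not > 2, and 1 < 2 | blocked: 3 > 2 |
| (2, 0) | not blocked | not blocked |
| (1, 1) | not blocked | not blocked |
| (0, 1) | not blocked | not blocked |
| (1, 2) | blocked: 2 Grade 3 | blocked |
| (3, 1) | blocked: 3 > 2 | blocked |

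**Enumeration.** The number of pairs with *a* + *b* ≤ *n* is (*n*+1)(*n*+2)/2.

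- For *n* = 12 this is 13 × 14 / 2 = 91. For *n* = 11 it is 12 × 13 / 2 = 78.
- The written rule leaves *a* in {0, 1, 2} with *b* in {0, 1} unblocked: 3 × 2 = 6 states at either *n*.
- Call a state inverted if it is unblocked but has at least as many subjects at Grade 2 or above, and at Grade 3 or above, as some blocked state. Only (2, 1) qualifies, against (3, 0).
- Counting Grade 2 or higher leaves 5 states unblocked and none inverted. Only (2, 1) changes.

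**How often the state might arise.** The documents give no ISR rates, so the rates below are assumptions for illustration, with subjects treated as independent. For *n* = 12:

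P(2, 1) = 12!/(2! 1! 9!) × p₂² × p₃ × (1 − p₂ − p₃)⁹ = 660 × p₂² × p₃ × (1 − p₂ − p₃)⁹

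| p₂ (Grade 2 at 168 h) | p₃ (Grade 3 at 168 h) | P(2, 1) |
|---|---|---|
| 2% | 0.5% | 0.0011 |
| 5% | 1% | 0.0095 |
| 10% | 2% | 0.0418 |
| 20% | 5% | 0.0991 |

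These are chances, per 12-subject cohort, of meeting the gap. They are not chances of wrongful escalation. At 10% and 2%, the chance that some rule is tripped would rise from 0.132 to 0.174 under the revised count, a difference equal to P(2, 1).

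**Mixed recovery.** With *k* affected subjects there are *k* + 1 possible recovery counts, and the text addresses only 0 and *k*. For *k* = 3, 2 of the 4 have no stated next step. The hold stands in both, because release requires all to recover.

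**The case against.** The strongest objection is that no subject is escalated because of the gap. The SRC must recommend each step after reviewing all available safety data. It may wait beyond 168 hours, and it may choose a reduced dose for Cohorts 3 and 4 without an amendment. This stands, and it limits the consequence to a mandatory hold becoming discretionary. But the protocol chose to bind the SRC on ISRs, and the binding fails where it is more needed. The committee consists of sponsor functions and the Investigator (Section 6.7), which gives a written limit added value.

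Second, a reaction still at Grade 3 after seven days might be classed as serious. Appendix 3 describes Grade 3 as incapacitating and lists persistent incapacity among the SAE criteria, and one related SAE blocks escalation. Some cases would be caught this way. The same appendix states that severity alone does not make an event serious, so the rule should not depend on it.

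Third, the Grade 3 rule has no time limit and covers any related Grade 3 event. A second subject with such an event, even one already resolved, would block escalation. The probabilities above are therefore upper bounds under their assumed rates. The higher rates also sit poorly with the protocol's account of rHuPH20 reactions as mostly mild and transient (Section 4.3), although this combination is untested.

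Finally, Grade 2 might be read as Grade 2 or higher. The text does not say so, and the section handles Grade 3 under a separate rule. Nor can a lone Grade 3 reaction be taken to block escalation because it is not on the permitted list. By that reading a single unresolved Grade 2 reaction would block too, and the threshold of more than 2 would mean nothing.

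**Conclusion.** The concern holds. As written, the ISR rule gives the wrong ordering at exactly one point, whether 11 or 12 subjects are reviewed. This rests on the literal text, and on the Grade 3 reaction being nonserious and the only related Grade 3 event in the cohort. The size is one state at each of two escalation decisions, with a frequency the documents do not allow to be estimated. SRC judgement remains as a safeguard, so this is a defect that should be corrected rather than one that invalidates the design. The mixed-recovery gap is minor: a next step is missing, but escalation stays barred.

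**What to change.** In Section 6.7.1, make two wording changes and carry them into the SRC charter:

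1. Count subjects whose ISRs are *still Grade 2 or higher* at 168 hours, keeping the threshold at more than 2. A reaction that has come down from Grade 3 to Grade 2 is then plainly included.
2. Have the post-extension provision apply when *any affected subject remains at Grade 2 or higher*, so that the SRC's two stated options also cover mixed recovery.

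Leave the Grade 3 and SAE rules alone. The protocol's tolerance of a single nonserious Grade 3 event is kept, since (0, 1) and (1, 1) stay unblocked. No subjects, visits or tests are added. The cost is that escalation is held in one further state, with observation extended by up to 168 hours before the SRC's options apply.
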